4.1.3 Exclusion Criteria

Subjects who meet any of the following criteria will be excluded from this study:

- Pregnancy (positive pregnancy test)
- Uncontrolled glaucoma on three medicines or more to control intraocular pressure
- Prior enrollment in the study
- Any other condition that the investigator believes would pose a significant hazard to the subject if the investigational therapy were initiated
- Participation in another simultaneous medical investigation or trial

4.2 METHOD OF TREATMENT ASSIGNMENT

The enrolled subjects will be randomized into two groups, 0.5 mg injection of ranibizumab or additional panretinal photocoagulation (PRP), in a two-to-one ratio (2:1). Randomization will occur by alternating treatment groups in the above ratio, as patients are included in the study. For example, Patient A and

Patient B will receive ranibizumab, Patient C will receive additional PRP, Patient D and Patient E will receive ranibizumab, etc. Therefore, seven (7) patients will receive ranibizumab and three (3) patients will receive additional PRP. There will be no masking of which treatment each patient receives.

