2. OBJECTIVES

2.1 Primary Objective

To compare the efficacy of ranibizumab versus additional panretinal photocoagulation on diabetic neovascularization that is persistent despite previous treatment with panretinal photocoagulation.

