3. STUDY DESIGN

3.1 DESCRIPTION OF THE STUDY

This is an open-label, Phase I/II study of intravitreally-administered ranibizumab in subjects with persistent (greater than three months) diabetic neovascularization previously treated with panretinal photocoagulation (at least 1200 or more 500- μ m burns).

Consented, enrolled subjects will either receive open-label intravitreal injections of 0.5-mg dose of ranibizumab or additional panretinal photocoagulation (up to 500 300-500 μ m laser spots) in a ratio of two-to-one (2:1) at the beginning of the study period. ETDRS best-corrected visual acuity, contrast sensitivity, and Optos color photography will be performed at enrollment, at weeks 1, 2, 3 and 4, and at months 2, 3, 4, 5 and 6. The subjects will undergo fluorescein angiography utilizing the Optomap FA (fluorescein angiography) system and optical coherence tomography (OCT) at enrollment, at weeks 2 and 4, and at months 2, 3, 4 and 6. The subjects will be followed for a 6-month period for stabilization, regression, or recurrence of

neovascularization. In addition, patients will be evaluated for occurrence of macular edema.

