3.3 OUTCOME MEASURES

- **3.3.1 Primary Outcome Measures**

The primary efficacy outcome measures include:

- The percentage change of the area of the patient's neovascularization as measured in pixels by Optomap FA
- The percentage change of macular edema measured by retinal thickness by OCT

The primary safety and tolerability outcome measures are:

- Incidence and severity of ocular adverse events, as identified by ophthalmic examination
- Incidence and severity of other adverse events, as identified by physical examination, subject reporting, and changes in vital signs

- **3.3.2 Secondary Outcome Measures**

The secondary outcome measures are:

- Mean change in Best Corrected Visual Acuity (BCVA), as assessed by the number of letters read correctly on the ETDRS eye chart at a starting test distance of 4 meters 3 and 6 months
- Percentage of patients gaining 3 or more lines of vision according to ETDRS eye chart testing
- Occurrence rate of proliferative diabetic complications including vitreous hemorrhage, iris neovascularization and tractional retinal detachment

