4. MATERIALS AND METHODS

4.1 SUBJECTS

4.1.1 Subject Selection

Ten (10) subjects from one site in the United States will be enrolled. Eligible subjects will have provided informed consent. (See Appendix A, the study flow chart, for screening assessments.)

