APPENDIX A: Study Flowchart

	Enrollment	1 week	2 weeks	3 weeks	4 weeks	2 months	3 months	4 months	5 months	6 months	14 days after withdrawal
Informed consent	X										
Demographic data	X										
Hemoglobin A _{1c}	X										
Urine Pregnancy Test	X										
Physical examination and medical history	X										
Vital signs	X	X	X	X	X	X	X	X	X	X	X
Intraocular Pressure	X	X	X	X	X	X	X	X	X	X	X
Slit-lamp exam	X	X	X	X	X	X	X	X	X	X	X
Dilated binocular indirect ophthalmoscopy	X	X	X	X	X	X	X	X	X	X	X
Ranibizumab treatment	X*										
Finger count vision after injection	X										
Panretinal photocoagulation	X*										
Telephone Safety Check	X + 2 Days										
SAE monitoring	X	X	X	X	X	X	X	X	X	X	X
ETDRS BCVA at 4 meters	X	X	X	X	X	X	X	X	X	X	X
Contrast sensitivity testing	X	X	X	X	X	X	X	X	X	X	X
Optomap FA	X	X				X	X	X	X	X	X
Optical Coherence Tomography	X		X			X	X	X	X	X	X
Optos color photos	X	X	X	X	X	X	X	X	X	X	X

* Patients will be treated with either ranibizumab or PRP, depending upon randomization

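### Section 4.2 and the Appendix A footnote call a fixed alternation randomization; nothing in it is random or concealed, and the next arm is always known before a patient is included

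*Protocol*

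**What the plan says.** Section 4.2 of the protocol opens with "The enrolled subjects will be randomized into two groups", in a 2:1 ratio of ranibizumab to additional PRP. The next sentence gives the mechanism: "Randomization will occur by alternating treatment groups in the above ratio, as patients are included in the study". The example has Patients A and B on ranibizumab, C on PRP, D and E on ranibizumab, and so on. The section derives seven ranibizumab and three PRP patients from this pattern and closes with "There will be no masking of which treatment each patient receives".

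The Appendix A footnote repeats the label: "Patients will be treated with either ranibizumab or PRP, depending upon randomization".

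The primary objective (2.1) is a comparison between arms: "To compare the efficacy of ranibizumab versus additional panretinal photocoagulation on diabetic neovascularization". On size and setting, section 4.1.1 says: "Ten (10) subjects from one site in the United States will be enrolled". Section 4.8.3 plans no formal efficacy analysis. No section describes a random sequence, a random start, assignment by a third party, sealed envelopes or any other concealment.

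**The concern.** Random assignment needs a chance element, and alternation has none. The protocol therefore claims a property that its own mechanism lacks. This is not a detail left for a statistical analysis plan: section 4.2 fixes the mechanism and misnames it.

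The foreknowledge also matters. At one unmasked site, whoever includes patients knows the next arm, and the arm depends only on the order of inclusion. The entry criteria leave that order open:

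- Section 4.1.2 requires neovascularization that has persisted at least three months, with no upper limit on duration and no limit on area.
- Eligibility rests on a fluorescein angiogram, so the lesion is seen before inclusion.
- Section 4.1.3 has an exclusion that rests on the investigator's judgement of hazard.

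The first primary outcome is "The percentage change of the area of the patient's neovascularization as measured in pixels by Optomap FA", so what the angiogram shows before inclusion bears on the baseline of that outcome. The timing or choice of inclusion could depend on the next arm. With three PRP patients, one changed assignment alters a third of the comparator arm. A report that takes over the protocol's label would present the comparison as randomized when it is not.

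**Working it through.** **Inputs.** 10 subjects at one site (4.1.1); 2:1 alternation in order of inclusion, the example for Patients A to E, arm sizes 7 and 3, no masking (all 4.2). R = ranibizumab, P = PRP.

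**1. The plan's own figure.** Repeating the cycle R, R, P over 10 inclusions gives R R P R R P R R P R: 7 R and 3 P, with P at places 3, 6 and 9. This reproduces the stated arm sizes.

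**2. Predictability as written.** There is one sequence, so 10 of 10 assignments and 3 of 3 PRP places are known before inclusion. This takes the example as binding, although it is introduced only as an example. The other starting points of the cycle are:

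- P, R, R gives 6 R and 4 P, which contradicts the stated 7 and 3.
- R, P, R gives 7 R and 3 P, with P at places 2, 5 and 8.

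If the start were open between the two cycles that fit 7 and 3, only the 2nd assignment would be uncertain, and everything after it would be known.

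**3. Effect of the order of inclusion.** The nine adjacent pairs are RR, RP, PR, RR, RP, PR, RR, RP, PR. In 6 of 9 the arms differ, so exchanging two eligible patients exchanges their treatments. Every P has an R directly before and after it, so including one other patient first moves a patient due for PRP to ranibizumab.

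**4. Comparison: a concealed random order of 7 R and 3 P**, with past assignments visible and totals known. There are C(10,3) = 120 equally likely orders. Place k is known with certainty when only one arm is left, which happens in C(k−1,3) + C(k−1,7) orders:

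| Place | 1–3 | 4 | 5 | 6 | 7 | 8 | 9 | 10 |
|---|---|---|---|---|---|---|---|---|
| Orders of 120 | 0 each | 1 | 4 | 10 | 20 | 36 | 64 | 120 |

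- Average number known: 255/120 = 2.125 of 10.
- PRP places known, the C(k−1,7) part: (1 + 8 + 36)/120 = 45/120 = 0.375 of 3.
- Late places: 8th 36/120 = 30%, 9th 64/120 = 53%, 10th always.

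**5. A second measure: best guess.** Enumerating the 120 orders, someone who knows the totals and the past assignments guesses the next arm correctly 7.47 times in 10 on average. Under alternation the figure is 10. Always guessing ranibizumab is right 7 times in 10, because of the 7:3 split alone. The gain from knowing the scheme is therefore 10 − 7 = 3 correct guesses under alternation and 7.47 − 7 = 0.47 under the concealed order.

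**6. Price of a random order if enrolment stops early** (4.7 allows this). P(no PRP among the first 5) = C(7,5)/C(10,5) = 21/252 = 8.3%. Alternation gives 4:1 at that point.

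**The case against.** The strongest reply accepts that the label is wrong but gives it little weight.

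- **It is a ten-patient pilot with no formal efficacy analysis, and the method is disclosed with an example.** True. A report that reproduced 4.2 in full would also reveal the alternation. But the primary objective remains a comparison of efficacy, and without a formal analysis its description is what readers rely on. Random assignment of 7 and 3 could not be relied on to balance lesion area either; it would remove foreknowledge, not chance imbalance.
- **The contrast of 10 with 2.125 flatters the alternative, since a good guess also helps someone steer inclusion.** This is fair, and 7.47 should stand beside 2.125. Most of the 7.47 comes from the 7:3 split itself, and PRP places fall from 3 of 3 known with certainty to 0.375 of 3.
- **The selection route is thin.** Exchanging patients needs two candidates at once, or a deferral. Completion within 12 months (4.8.1) with 6 months of follow-up (3.1) leaves about 6 months for ten inclusions, and nothing shows a queue of candidates. This stands: selection is something the design permits, not something shown.
- **The rest of the protocol does not contradict the label.** Largely so. Section 3.1 says only "This is an open-label, Phase I/II study of intravitreally-administered ranibizumab" and gives the 2:1 ratio. Section 4.8.1 mentions a randomized trial as a possible later step and does not call this one non-randomized. The finding does not depend on either section.

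**Conclusion.** The concern holds and should be fixed. The certain error is the label, in two places in 4.2 and one in Appendix A. With it comes full foreknowledge: 10 of 10 assignments if the example is followed, or all but the 2nd if the start of the cycle is left open. The absence of concealment is inferred from silence, but unmasked alternation at one site cannot be concealed from the person who includes patients.

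No size of bias is claimed, because the protocol gives no basis for one, and no error rate is affected. What changes is how the descriptive 7-versus-3 comparison may be presented. The wording can be corrected at any time, and an amendment could randomize patients not yet included. Assignments already made stay non-random.

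**What to change.** **Preferred: make the assignment random.** In 4.2, replace the alternation sentence and the Patient A to E example with:

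*Assignments follow a computer-generated random order of 7 ranibizumab and 3 PRP, prepared by a person who does not enrol patients and kept in sequentially numbered, sealed, opaque envelopes. The next envelope is opened only after consent and confirmed eligibility are recorded; from that point the patient counts as included.*

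Delete *Therefore* from the next sentence, since the arm sizes no longer follow from a pattern.

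Costs:

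- One paragraph, ten envelopes and one person outside enrolment. That such a person is available is an assumption; the protocol does not say who enrols.
- Late assignments stay partly deducible, and the ratio may drift if enrolment stops early (figures above).
- The time of opening must be reconciled with treatment at enrollment (4.3.2, 4.5.1) and with the three days of antimicrobials before treatment (Appendix B). Under alternation the arm is known ahead of those days; under a concealed order it is not. No clinical rule is proposed here. If the envelope is opened days before the treatment visit, some enrollment measurements may be taken with the arm known.

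**Fallback: keep alternation and name it correctly.**

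- Replace the first two sentences of 4.2 with: *Enrolled subjects will be assigned, without randomization, to ranibizumab or additional PRP by alternation in a 2:1 ratio in order of inclusion.* Leave the dose wording unchanged and keep the example.
- End the Appendix A footnote with *depending upon the alternating assignment*.
- Add to 4.8.3 that the between-arm comparison is non-randomized and descriptive.

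This costs two rewritten sentences, one footnote and one added sentence. It corrects the label but leaves the foreknowledge. Under either option, the mentions of randomization in 1.5.3 (another study) and 4.8.1 (a later trial) stay as they are.

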4.3 STUDY TREATMENT

- 4.3.1 Formulation**

Ranibizumab is formulated as a sterile solution aseptically filled in a sterile, 3-mL stoppered glass vial. Each vial contains 0.5 mL of 10mg/mL (0.5-mg dose level) ranibizumab aqueous solution (pH 5.5) with histidine, trehalose, and polysorbate 20. The vial contains no preservative and is suitable for single use only.

For further details and molecule characterization, see the Investigator Brochure.

4.3.2 Dosage, Administration, and Storage

- a. Dosage**

0.5-mg of ranibizumab will be injected intravitreally at the patient's enrollment in the study for patients in the ranibizumab treatment group.

- b. Administration**

**See Appendix B for detailed pre-injection procedures.*

- c. Storage**

Upon receipt, study drug kits should be refrigerated at 2°C - 8°C (36°F - 46°F). DO NOT FREEZE. Do not use beyond the expiration date. Ranibizumab vials should remain refrigerated. Protect vials from direct sunlight.

VIALS ARE FOR SINGLE USE ONLY. Vials used for one subject may not be used for any other subject.

4.4 CONCOMITANT AND EXCLUDED THERAPIES

Subjects may continue to receive all medications and standard treatments administered for their conditions at the discretion of their treating physician.

4.5.2 Early Termination Assessments

Subjects who withdraw from the study prior to completion should return for an early termination evaluation 14 days (\pm 7 days) following the last injection/study visit for monitoring of all adverse events (serious and nonserious). The schedule of assessments for early termination is the same as that for the final visit.

4.6 SUBJECT DISCONTINUATION

Subjects have a right to withdraw from the study at any time.

The subject may be withdrawn from the study for any reasons: if it is in the best interest of the subject, intercurrent illness, adverse events, or worsening

condition. Rush University Medical Center may request the withdrawal of a subject because of protocol violations, administrative reasons, or any other valid and ethical reasons.

Subjects will be discontinued and receive standard additional panretinal photocoagulation for development of neovascular glaucoma (NVG).

Other reasons for subject discontinuation may include, but are not limited to, the following:

- Sensory rhegmatogenous retinal detachment or Stage 3 or 4 macular hole
- Investigator determination that it is not in the best interest of the subject to continue participation
- Pregnancy
- Verteporfin PDT treatment in the study eye
- Pegaptanib sodium injection treatment in either eye
- SAE
- Any other safety concerns

If a subject discontinues or is discontinued from the study, he or she will not be allowed to re-enter the study.

In the event of an adverse event in the study eye that is considered by the investigator to be severe in intensity, serious consideration should be given to discontinuing the subject from the study.

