5.5 PROCEDURES FOR RECORDING AND REPORTING ADVERSE EVENTS

• 5.5.1 Recording Adverse Events (see examples below)

To improve the quality and precision of acquired AE data, investigators should observe the following guidelines:

- Whenever possible, use recognized medical terms when recording AEs on the AE pages of the CRF. Do not use colloquialisms and/or abbreviations.
- If known, record the diagnosis (i.e., disease or syndrome) rather than component signs and symptoms on AE pages of the CRF (e.g., record congestive heart failure rather than dyspnea, rales, and cyanosis). However, signs and symptoms that are considered unrelated to an encountered syndrome or disease should be recorded as individual AEs on the CRF (e.g., if congestive heart failure and severe headache are observed at the same time, each event should be recorded as an individual AE).
- AEs occurring secondary to other events (e.g., sequelae) should be identified by the primary cause. A “primary” AE, if clearly identifiable, generally represents the most accurate clinical term to record on AE pages of the CRF. If a primary serious AE (SAE) is recorded on an SAE CRF, events occurring secondary to the primary event should be described in the narrative description of the case.

For example:

Orthostatic hypotension → Fainting and fall to floor → Head trauma → Neck pain

The primary AE is orthostatic hypotension.

- **5.5.2 Serious Adverse Events**

An AE occurring **at any dose** (including overdose) should be classified as **SERIOUS** if:

- It resulted in death (i.e., the AE caused or led to death).
- It was life threatening (i.e., the AE placed the subject at immediate risk of death; it does not apply to an AE that hypothetically might have caused death if it were more severe).
- It required or prolonged inpatient hospitalization (i.e., the AE required at least a 24-hour inpatient hospitalization or prolonged a hospitalization beyond the expected length of stay; hospitalizations for elective medical/surgical procedures, scheduled treatments, or routine check-ups are not SAEs by this criterion).
- It was disabling (i.e., the AE resulted in a substantial disruption of the subject's ability to carry out normal life functions).
- It resulted in a congenital anomaly/birth defect (i.e., an adverse outcome in a child or fetus of a subject exposed to the molecule or study drug prior to conception or during pregnancy).

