- It does not meet any of the above serious criteria but may jeopardize the subject or may require medical or surgical intervention to prevent one of the outcomes listed above.

SAE Reporting

Investigators must report all SAEs to Genentech within 48 hours of observing or learning of the event. For initial SAE reports, investigators should record all case details that can be gathered within 48 hours on the SAE page of the CRF.

The completed SAE page and SAE Fax Cover Sheet should be faxed immediately upon completion to the Genentech Drug Safety at:

[contact]

or

[contact]

Relevant follow-up information should be submitted to Genentech as soon as it becomes available.

- **5.5.3 Special Reporting Situations**

- a. **Death**

Death is an outcome of an event. The **event** that resulted in the death should be recorded and reported on the SAE pages of the CRF.

- b. **Hospitalizations for Surgical or Diagnostic Procedures**

The **illness** leading to the surgical or diagnostic procedure should be recorded as the SAE, not the procedure itself. The procedure should be captured in the case narrative as part of the action taken in response to the illness.

- c. **Pregnancy**

- **5.5.4 Type And Duration Of Follow-Up After Adverse Events**

All reported AEs should be followed until resolution or until the subject's participation in the study ends. Subjects who have an ongoing study drug-related SAE at study completion or at discontinuation from the study will be followed by the investigator or his or her designee until the event is resolved or determined to be irreversible, chronic, or stable by the investigator.

- **5.5.5 Regulatory Reporting Requirements for Principal Investigators Holding Their Own INDs**

Investigators conducting studies under their own INDs are responsible for expedited Safety Reports and IND Annual Reports to the FDA.

Expedited IND Safety Reports:

For this **Investigator Sponsored IND Study**, some additional reporting requirements for the FDA apply in accordance with the guidance set forth in 21 CFR § 312.32.

Events meeting the following criteria should be submitted to the Food and Drug Administration (FDA) as expedited IND Safety Reports according to the following guidance and timelines:

Fatal or Life-Threatening, Unexpected, Drug-related SAEs

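### Both arms are treated only at enrollment, so leaving the study for a safety reason cannot reduce exposure to study treatment, but it cuts short safety follow-up of every event except ongoing drug-related SAEs

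*Protocol*

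**What the plan says.** **Treatment.** Section 3.1 assigns ranibizumab or additional panretinal photocoagulation (PRP) "in a ratio of two-to-one (2:1) at the beginning of the study period". Section 4.3.2 states that "0.5-mg of ranibizumab will be injected intravitreally at the patient's enrollment in the study". Section 4.5.1 and Appendix A place both treatments at the enrollment visit and nowhere else.

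**Leaving the study.** Section 4.6 introduces its list with "Other reasons for subject discontinuation may include, but are not limited to, the following"; the list includes SAEs and any other safety concern. For a study-eye AE that the investigator grades severe, "serious consideration should be given to discontinuing the subject from the study". A patient who leaves is told that "he or she will not be allowed to re-enter the study". The section does not distinguish leaving treatment from leaving follow-up.

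**What happens after exit.**
- Section 4.5.2 asks for one early-termination evaluation, 14 days (± 7) after the last injection or study visit, with the final-visit assessments.
- Section 5.1 adds a contact for AEs 7 days after the last injection or study visit. It closes the AE recording window at the last study visit.
- Section 5.5.4 opens with the general rule, "All reported AEs should be followed until resolution or until" the patient's participation ends. It then makes one exception: an SAE related to study drug and still ongoing at discontinuation is followed until it has resolved or is judged irreversible, chronic or stable.

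**Use of the data.** Section 3.3.1 makes the incidence and severity of ocular and other AEs the primary safety outcomes. Section 4.8.4 bases the safety analysis on available cases, with no imputation.

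**The concern.** Where dosing is repeated, stopping because of an AE limits further exposure. Here the only dose or laser session has already been given when any on-study AE occurs, so there is no later study treatment to withhold. Yet Section 4.6 takes the patient out of the study, not off treatment, and the general rule in Section 5.5.4 then ends AE follow-up.

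What is at stake is the later part of the safety record in the patients whose events prompted the exit: how long the event lasted, how it ended, and whether anything else followed. The loss is selective, because it falls on patients with safety problems, and available-case summaries do nothing to correct it. It is also uneven between arms. The exception for continued follow-up is tied to study drug, and Section 5.1 assesses causality against study drug only, so an SAE caused by PRP does not qualify.

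**Working it through.** The protocol gives no figure to reproduce on this point and states that it made no sample size calculation. The check compares the sections and adds day arithmetic.

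**Step 1: can exit reduce exposure?** Sections 3.1, 4.3.2 and 4.5.1 and Appendix A agree on one treatment, at enrollment, in each arm. Some wording suggests repeated dosing (injections in the plural in Section 3.1, serial injections in Appendix B), but the dosage section and the flowchart settle the matter. Exposure to study treatment is complete before any exit.

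**Step 2: which events are still followed after exit?** Read together, Sections 4.5.2, 5.1 and 5.5.4 give:

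| Event at exit | 7-day contact and early-termination visit | Followed beyond that |
|---|---|---|
| Ongoing SAE related to study drug | Yes | Yes, until resolved or judged irreversible, chronic or stable |
| SAE judged unrelated to study drug | Yes | No |
| SAE related to PRP | Yes | No |
| Non-serious AE, including one graded severe | Yes | No |
| New event starting later | Only if it has begun by then | No |

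**Step 3: how much scheduled observation is lost?**

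Inputs: planned follow-up of 6 months (Section 3.1), taken as 6 × 365.25 / 12 = 182.6 days; last regular visit on day d; early-termination visit at d + 14 ± 7, that is, from d + 7 to d + 21 (Section 4.5.2).

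Share lost = (182.6 − early-termination day) / 182.6.

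| Last regular visit | Early-termination day | Days lost | Share lost |
|---|---|---|---|
| Week 1 (d = 7) | 14 to 28 | 155 to 169 | 85% to 92% |
| Week 4 (d = 28) | 35 to 49 | 134 to 148 | 73% to 81% |
| Month 3 (d = 91) | 98 to 112 | 71 to 85 | 39% to 46% |

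For week 1: (182.6 − 28) / 182.6 = 84.7% and (182.6 − 14) / 182.6 = 92.3%.

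**Step 4: weight of one patient.** Section 4.2 gives 7 patients on ranibizumab and 3 on PRP. One early exit is 1/7 = 14% of the drug arm or 1/3 = 33% of the PRP arm.

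**The case against.** Several arguments on the other side have force.

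- **Follow-up does not simply stop at exit.** A reader might infer from the first sentence of Section 5.5.4 that it does. The exception in the next sentence covers ongoing drug-related SAEs, and every patient who leaves early is due a contact and a visit with full final-visit assessments. This stands, and it confines the point to the other events in Step 2.
- **Severe events will often be serious.** Section 5.1 defines severe as incapacitating, and Section 5.5.2 counts a substantially disabling event as serious. Many severe study-eye AEs on ranibizumab would then be drug-related SAEs and still be followed. This narrows the severe but non-serious group. It does not help unrelated SAEs or any PRP-related SAE.
- **Exit for these reasons is discretionary.** The investigator may keep the patient on the full schedule. This affects how often the gap occurs, but for severe study-eye AEs the text leans toward removal.
- **Exit does more than end observation.** It also ends study procedures, such as repeat fluorescein angiography. This is correct, so removal cannot be called pointless.
- **The event that prompts exit has already been recorded and graded.** Its incidence, and its severity to date, are therefore kept. A reader might infer that the safety summary will look cleaner than the truth. The documents do not show that; they show that later course and later events can be missed.
- **Pregnancy.** Because pregnancy is listed as a reason to leave, a reader might infer that birth outcomes are lost through discontinuation. The pregnancy heading in Section 5.5.3 has no text in the available copy, possibly because it was lost in conversion. A term birth after conception on study would also fall after month 6 whether or not the patient left. No conclusion is drawn.

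**Conclusion.** The point holds in a limited form. Because each arm is treated once, at enrollment, a later safety-driven exit cannot reduce exposure to study treatment. It does shorten observation of non-serious AEs, of SAEs judged unrelated to study drug and of PRP-related SAEs, and it leaves later events in those patients unrecorded. Ongoing drug-related SAEs are still followed, although the patient's other scheduled assessments end.

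The size depends on when the patient leaves: most of the planned follow-up is lost after exit in the first month, and somewhat under half after exit at month 3. No single percentage is typical, and the documents give no basis for predicting how many of the 10 patients would leave. With arms of 7 and 3, one patient is enough to matter.

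The figures assume that 6 months is about 183 days, that the early-termination visit takes place within its window, and that no informal follow-up occurs outside the protocol.

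**What to change.** Reconcile Sections 4.5.2, 4.6, 5.1 and 5.5.4 along these lines:

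1. In Section 4.6, separate withdrawal of consent from exit for an AE, an SAE or another safety concern.
2. Unless consent is withdrawn, continue to collect AE and safety data at the visits already planned through month 6, in both arms. State that study imaging such as angiography is not required at these visits and is left to the investigator.
3. In Section 5.5.4, extend the follow-up rule that applies after exit to AEs that prompted the exit and to PRP-related SAEs. Use the end point already written there (resolved, or judged irreversible, chronic or stable), so that the duty is not open-ended.
4. Align Sections 4.5.2 and 5.1 with this, so that the early-termination visit and the 7-day contact are the minimum for patients who withdraw consent but agree to return, and the AE window stays open for those who remain in safety follow-up.

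The cost is a protocol amendment. The visits are already planned for all 10 patients, so the only burden is a few more visits for patients who would otherwise have left, and occasional follow-up of an unsettled event past month 6. The change concerns data collection only; nothing about treatment or clinical management is proposed.
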